A RANDOMIZED TRIAL OF THE SYNC APP

Protocol Number: UMCC 2020.157

National Clinical Trial (NCT) Identifier: NCT04827446

Principal Investigator: [name] [name], MS
[name]
[name]
[contact]
[contact]
Email: [contact]

Co-Investigators: [name] PhD, [name] MD PhD, [name]
MD, [name] PhD, [name] MD PhD

Biostatistician: [name] PhD
[contact]
Email: [contact]

Single Center: University of Michigan

Version: April 4, 2022

Table of Contents

PROTOCOL SYNOPSIS	3
STUDY SCHEMA: SCHEDULE OF EVENTS	6
TIME AND EVENTS TABLE	7
INTERVENTION ARM VS CONTROL ARM	8
1. BACKGROUND AND SIGNIFICANCE	9
2. STUDY DESIGN	13
3. STUDY ENDPOINTS	17
4. PATIENT ENROLLMENT AND EVALUATION	18
5. STATISTICAL CONSIDERATIONS	20
APPENDIX A: DESCRIPTION OF DEVICES	23
Fitbit Charge 3	30
Apple Watch	36
APPENDIX B: SYNC COMPONENTS	51
APPENDIX C: USER-REPORTED OUTCOME MEASURES	62
APPENDIX D: REFERENCES	60

PROTOCOL SYNOPSIS

A RANDOMIZED TRIAL OF THE SYNC APP

Principal Investigator: [name]

Study Design: This is a study to assess whether individually tailored lighting and behavioral interventions delivered through an app are able to reduce symptoms of fatigue and improve quality of life across three populations of cancer patients. We will recruit 138 patients (69 control, 69 interventional) across three cancer populations: breast cancer and prostate cancer, and patients who have undergone hematopoietic stem cell transplant (HSCT). Participants will be randomized 1:1 to either the interventional SYNC app or to a control app.

Primary Objective: The primary objective is to test the statistical significance or difference between the intervention arm and the control arm in the measured outcome of fatigue, as quantified by daily fatigue surveys and weekly PROMIS Short Form v. 1.0 Fatigue 4a surveys.

Secondary Objective: The secondary objective will be to assess user sleep disturbances, anxiety, depression, physical function, and global health via a suite of PROMIS questionnaires.

Exploratory Objectives: Exploratory objectives will be to assess: i) physical activity through physiological data capture using the wearable sensor; ii) health care utilization (i.e., total count of hospital days, ED visits, readmissions, and ambulatory care clinic visits), and iii) sleep aid usage, as measured by self-report.

Eligibility Criteria: All patients will be outpatient, though most will still be undergoing long-term treatment: breast cancer patients often receive endocrine therapy; prostate cancer patients often receive androgen deprivation therapy; and HSCT patients will be recovering their immune system from the high-dose chemotherapy that was administered in preparation for their transplant. We will exclude patients actively receiving chemotherapy at the time of enrollment to avoid potential confounding factors. However, post-transplant maintenance chemotherapy will be allowed. We will also exclude night shift workers, where night shift work is defined as working a significant number of hours (i.e. more than half) between the hours of 11PM and 6AM on a regular basis. Participants will be required to be able to read and write English, be at least 18 years old, and report their baseline fatigue level as

moderate (4 or higher on a 10-point scale). Patients must own an iPhone 6s or later (with iOS 14 or later, or willing to update to iOS 14+) and be able to complete surveys on it, or they must agree to utilize a loaner iPhone provided by the study team to use during the study and return at the end of the study.

Treatment Description: All participants will be given access to an app into which they enter their research ID number. The research ID number will determine which version of the app is loaded on their phone. Participants will also be given a wearable device and a pair of glasses. Interventional group participants will be given a pair of blue light-blocking glasses. Participants in the control group will be given a pair of glasses that does not block visible light. All participants will wear the wearable device day and night over the course of the 12-week trial. Participants in the interventional group will use a version of the app that gives them personalized lighting recommendations (e.g. "Seek bright light") and a time interval over which the recommendation applies (e.g. "8:30 - 9:45 am").

Control arm: Control group participants will use a version of the app that makes recommendations to use the glasses; however, the time intervals recommended will be chosen to occur in the period of time when any change in lighting is expected to have no effect on the circadian clock (e.g. around noon, for many people already entrained to a diurnal schedule). Participants will be informed that they should only wear the glasses if it is reasonable for them to do so.

Accrual Objective: We will enroll 138 cancer patients, with half in the intervention arm and half in the control arm. Our primary endpoint is the PROMIS 4-item Fatigue Short Form. The age- and sex-adjusted norm for the Fatigue scale is 50 points, with a standard deviation of 10 points. These statistics have been shown to be largely generalizable to the cancer patient population (mean: 52, standard deviation 7.6). Our study will have power of 0.80, assuming a two-sided Type I error rate of 0.05, to detect an effect size of half the standard deviation between the intervention and control arms if 64 cancer patients are enrolled in each of the control and intervention groups. A mean difference of one-half a standard deviation is clinically meaningful and is considered a medium effect size for clinical trials. During the primary analysis, we will adjust for the fact that there are three cancer populations in our data and will look for a well-defined effect that is marginal within each population. We will accrue a total of 69 patients in each arm to account for attrition of data, assuming a 7% dropout rate from the trial.

Accrual Period: The estimated accrual period is 1.5 years

Study Duration: Data will be collected from participants for 12 weeks. Passive collection of wearable data through the app will continue for up to one year for each participant who opts-in to continue using the app, and medical records may be accessed for up to five years after the conclusion of the 12-week collection period.

STUDY SCHEMA: SCHEDULE OF EVENTS

[figure not shown]

Diagram outlining the survey data collected over the trial. Note: "Control actions" here refers to following "dummy" lighting recommendations that are minimally expected to affect the circadian clock.

TIME AND EVENTS TABLE

Patient Events Timeline			
Every day after starting the trial:	Every week, starting on the first day of the trial:	On the first day and last day of the trial:	At any point in time:
Single question daily fatigue survey	PROMIS Fatigue survey, "How is your experience with the app?" questionnaire, sleep aid usage survey	PROMIS Sleep, Anxiety, Depression, Physical Function, Global Health	App experience free response

Study Timeline	Year 1				Year 2			
	Q1	Q2	Q3	Q4	Q1	Q2	Q3	Q4
Revise the app to include the capacity to collect survey responses	X	X						
Begin identifying potential subjects using UofM Health Research website		X						
Rolling recruitment, consent, and randomization from all three cancer groups			X	X	X	X	X	
Re-evaluate study protocol based on the first cohort of participants				X	X			
Data processing			X	X	X	X	X	X
Data analysis				X	X	X	X	X
Manuscript preparation				X	X	X	X	X

Intervention Arm vs Control Arm

Intervention Arm

Wearable sensor:

Patient is given a wearable device to wear for 12 weeks.

Blue-blocking glasses:

Patient is given blue-blocking glasses to wear at instructed times.

Full SYNC app:

Patient downloads the SYNC app and is given light interventions designed to have a targeted, personalized effect on the circadian clock.

Control Arm

Wearable sensor:

Patient is given a wearable device to wear for 12 weeks.

Clear glasses:

Patient is given glasses that block no visible light.

[figure not shown]
“Dummy” SYNC app:

Patient downloads the SYNC app and is given light interventions designed to have minimal impact on the circadian clock.

1. BACKGROUND AND SIGNIFICANCE

- 1.1. **Circadian rhythms are chronically disrupted in cancer patients, leading to worsened symptoms and outcomes.** A growing body of evidence links circadian rhythms to human health and disease. These rhythms, which repeat approximately once a day and are kept in sync with the local environment by the timing of light exposure, face constant disruption in the modern era of artificial lighting and smartphones (Wittmann et al. 2006; Roenneberg et al. 2012; Parsons et al. 2015). Sleep, the behavior most famously under circadian control, is not the only process affected: these rhythms feature prominently in nearly every major function in the body, from immune response to metabolism (Eckel-Mahan and Sassone-Corsi 2013; McClung 2013; Paganelli et al. 2018). Yet despite increased awareness of their importance for human health, circadian rhythms are rarely targeted in clinical interventions.
- 1.2. **Light as a treatment for circadian disruption.** Light therapy, in which people intentionally expose themselves to bright light and/or avoid light at specific times of day, holds promise for reducing circadian rhythm disruption to improve symptoms such as fatigue. However, all intervention studies carried out so far have been one-size-fits-all, with a single light intervention of fixed timing and without real-time personalization to match an individual patient's day-to-day variation in circadian rhythm. Even with these limitations, breast cancer patients exposed to 30 minutes of bright light in the morning experience reduced desynchrony (Neikrug et al. 2012), mitigated fatigue (Ancoli-Israel et al. 2012), and protection from a significant decline in quality of life (QOL) (Jeste et al. 2013). Other studies have found blocking evening light led to improved sleep in healthy populations, though no comparable studies have been carried out in cancer patients (van der Lely et al. 2015, Burkhart and Phelps 2009).
- 1.3. **Tracking circadian rhythms has historically been challenging in real-world conditions.** There is great promise for lighting interventions as therapy, yet several hurdles stand in the way. The first is awareness. Many patients are unaware of the effects of light on their bodies and how these effects change over the course of the day. In addition, daily exposure to morning light requires habit-formation, which can be burdensome. Importantly, the timing of light interventions in previous work has never been tailored to match the individual's circadian rhythm, instead opting for catch-all instructions; e.g., "on awakening" or "in the morning." This is despite the fact that sleep and circadian rhythms are distinct processes, particularly in people experiencing irregular sleep and light exposure.
- 1.4. **Mathematical models and wrist-worn wearables can be used to predict circadian time.** The gold standard for estimating circadian time is the costly and time-consuming dim light melatonin onset (DLMO) test. This salivary assessment, which takes hours to collect and costs hundreds of dollars, has made personalizing circadian recommendations impractical in the past. Recent work by our group and others has suggested that circadian rhythms can be tracked by coupling mathematical models to wearable devices that measure activity, light and/or heart rate (Stone et al. 2019; Woelders et al. 2017; Huang et al., In revisions; Bowman et al., in preparation). Building on these methods, it is now possible to deliver light interventions tailored to the individual user, making them both more habit-building and more effective.
- 1.5. **Prior work: Embedding circadian algorithms in mobile apps.** In our previous work, our team developed a prototype mobile application, SYNC, which tracked the circadian

clock indirectly using wrist-worn wearable sensor data (i.e., minute-by-minute activity/steps and heart rate) as input. The SYNC app makes behavioral recommendations to correct circadian misalignment in patients. The general types of recommendations are: 1) When to seek and avoid light; 2) When to seek and avoid caffeine; 3) Ideal window for sleep. These recommendations are given with associated time periods and tailored to match the user's ability and desire to control their light exposure (e.g. the ability to wear blue-blocking glasses, or be exposed to very bright light) and home time zone. For example, the app will only recommend that the user avoid light by wearing blue-blocking glasses if they have marked that they are willing to use blue-blockers in the Settings page, and will only recommend caffeine timing if the person is a caffeine user.

Sample data from a patient wearing an Apple Watch. The x-axis is time and the y-axis is step count (top) and heart rate (bottom) as recorded by the Apple Watch.

1.6. **Preliminary data suggests strong potential for wearables.** To assess the viability of cancer participants using a wrist-worn wearable and lighting hardware, participants were given a version of the app that passively collected data from an Apple Watch device without making active recommendations, a smart-bulb that could be controlled by the app (to change color to dim red) and red-tinted, blue-blocking glasses, but no specific instructions on how to use these beyond a simple educational primer on how light affects sleep. Overall, users in our Phase I usability trial found the wrist-worn wearable extremely easy to set up (100% found it "Very easy" to Wear and Charge, and 75% found it "Very Easy" to sync with their phone, with the remaining 25% rating it as "Fairly Easy."). The most difficult hardware challenge was connecting the lightbulb, with one participant choosing not to set it up and one person marking it as "Neutral" difficulty. In summary, most participants did not find the hardware overly burdensome to set up. Clear daily patterns of activity and heart rate can be seen over the course of the collected data. While the feasibility of deploying wearables in a patient population was unclear before the usability trial, we found patients were willing and able to reliably wear the device.

1.7. **Study Rationale.** The scientific premise of this protocol stems from the literature presented in the Background and Significance and the large body of prior work by the study PI and Co-Is who have extensive experience examining the information needs of cancer patients. The SYNC app has been tested in one-on-one user interviews and for ease-of-use with lighting and wearable hardware; the next stage of its development is to incorporate greater scientific rigor. The heterogeneity of cancer types and experiences means that an intervention may be effective for one population and not for another. The work proposed in this specific aim is to test the SYNC app, in three separate populations of cancer patients. Patients will be randomized either to use the SYNC app, with its tailored recommendations for use with blue-blocking glasses, or to a control app without tailored recommendations and clear glasses.

1.8. **SYNC 1.0 Development.** The app was developed for iOS devices by Arcascope using a Phase I SBIR grant. A non-interventional version of the app was tested for usability in a prior study. The app was designed based on five in-depth interviews, assessed for usability in four recorded tests with the first prototype, and tested again by eight participants in a long-term study, along with hardware, including blue-blocking glasses and mobile-controlled smart-bulbs. The app was capable of syncing with smart-bulb devices, as well as registering when these devices were used. These features of the app were removed in response to user feedback that they did not like interfacing with the smart lightbulbs.

[figure not shown]

Diagram showing simulations of how the lighting recommendations shift the circadian clock. Purple is expected sleep window, yellow is time spent in light, black is time spent in darkness. (Left) A delayed circadian rhythm remains delayed in the presence of no interventions. (Center) A delayed rhythm with low sleep drive is synchronized by a blue-blocking glasses intervention. (Right) A delayed rhythm with high sleep drive is synchronized by an earlier bedtime and a mid-afternoon nap.

1.9. **Understanding circadian interventions.** To better explain the recommendations by the app, consider the case where a user on a habitual 11:00 pm to 7:00 am sleep schedule has been disrupted by staying up later than normal. The model will track that user's circadian state as disrupted, which is shown by the x variable from the limit cycle oscillator model in the figure above as a dashed red line, out-of-sync with the solid black line (again, x) of someone entrained to 16 hours of light and 8 hours of dark. Periods of light and dark

are marked as bands of yellow and black, respectively. Predicted windows of sleep (Phillips and Robinson 2007) are marked by purple bands. All simulations start at 11:00 am local time.

The app makes different recommendations based on the user's predicted sleep drive. If the user followed no intervention (leftmost plot), they would end the 24-hour period still out of sync with their target rhythm. If they had accrued a relatively low sleep drive in the days leading up to the disruption, the app would recommend they put on blue-blocking glasses at 8:15 pm, with an anticipated sleep onset at 10:50 pm. If they had a significantly higher sleep drive, the app would recommend a maximum nap opportunity of 1.5 hours between 12:30 and 2:00 pm, and a bedtime at 7:40 pm. For all these sample recommendations, times have been rounded to the nearest five-minute mark. While only two interventions are shown (for "low" and "high" sleep drive), there are many others that would be recommended for different sleep drives and different disruptions.

- 1.10. **Scientific Premise.** Fatigue is a major problem for cancer patients, and one that can persist long after treatment ends. Recent work has demonstrated that light therapy may mitigate or reduce fatigue levels in both cancer patients and cancer survivors. This protocol seeks to assess how lighting interventions distributed through a mobile app affect fatigue, sleep, and quality of life across three populations of cancer patients. Our strong preliminary data, coupled with the need to deliver an effective intervention in a population with severe circadian disruption form the scientific premise. *Our central hypothesis is that targeted, personalized light interventions will reduce fatigue in cancer patients.*

1. STUDY DESIGN

- 1.1. *Study Overview.* This study will use a two-arm randomized study design. Participants will be recruited across three cancer types. Each of the participants will be randomized to an active “intervention” arm (using the full SYNC app) or to a control arm (using a “dummy” version of the SYNC app that gives recommendations for light at times that should not significantly affect the circadian clock). The random allocation of participants to the treatment arm or control arm establishes the basis for testing the statistical significance or difference between the groups in the measured outcome (patient fatigue, assessed by a daily 1-question fatigue survey and the PROMIS 4-item Fatigue). Patient age, gender, and other prognostic baseline characteristics that could potentially confound an observed association, including those that are unknown or unmeasured, will be distributed equally, except through chance alone, through random assignment. Thus, this design is well-suited to our goal of assessing the efficacy of a mobile health intervention, SYNC, on participants.
- 1.2. *Primary Hypothesis.* The primary hypothesis is that a mobile-app delivered circadian intervention (SYNC) will reduce patient fatigue.
- 1.3. *Study Objectives*
 - 1.3.1. Primary Objective. To test the difference between the “intervention” (full SYNC app) arm and the control (limited SYNC app) arm in the measured outcome of patient fatigue, assessed by daily 1 question surveys and weekly 4-item PROMIS questionnaires over the course of 12 weeks.
 - 1.3.2. Secondary Objective. To determine the change in sleep disturbances, anxiety, depression, physical functioning, and global health through PROMIS questionnaires, between baseline and the 12-week assessment in both the control and intervention arms, and to look for differences in this change between the two arms.
 - 1.3.3. Exploratory Objectives
 - 1.3.3.1. Change in patient physical activity through physiological data capture using the wearable sensors in the control versus intervention arm.
 - 1.3.3.2. Change in patient health care utilization (e.g., total count of hospital days, readmissions, and ambulatory care clinic visits) in the control versus intervention arm
 - 1.3.3.3. Change in patient sleep aid usage in the control versus intervention arm.
- 1.4. *Participant Eligibility*
 - 1.4.1. Inclusion Criteria
 - 1.4.1.1. Able to provide informed consent and willing to sign an approved consent form that conforms to federal and institutional guidelines.
 - 1.4.1.2. Comfortable reading and speaking English.
 - 1.4.1.3. Must own an iPhone 6s or later (with iOS 14 or later or willing to update to iOS 14+) and be willing to complete surveys on it, per the protocol. Alternatively, patients without iPhones must be willing to use a loaner iPhone provided by the study team to use during the study and return at the end of the study.
 - 1.4.1.4. ≥ 18 years of age.

- 1.4.1.5. Sleep aid usage will be allowed as long as the patient has been on a stable dose for at least 4 weeks prior to enrollment and agrees to continue the same dose during the study.
- 1.4.1.6. A response of at least 4 on a 10-point scale (with 0 = not fatigued at all and 10 = extremely fatigued) to the question "How fatigued did you feel in the last four weeks?"
- 1.4.1.7. Breast cancer population: Diagnosed with stage 1-3 breast cancer in the last 10 years, without metastatic disease. Chemotherapy or radiation therapy, if indicated, must have been completed at least 3 months prior to enrollment. Concomitant anti-HER2 therapy and/or anti-endocrine therapy is permitted.
- 1.4.1.8. Prostate cancer population: Undergoing androgen deprivation therapy (ADT) for at least three months and are anticipated to remain on ADT for the duration of the trial. Concomitant additional anti-androgen therapy (e.g., enzalutamide) is permitted.
- 1.4.1.9. HSCT population: Participants must be from the University of Michigan Blood and Marrow Transplant Program.

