1.4.2. Exclusion Criteria

- 1.4.2.1. The patient cannot be undergoing chemotherapy at the time of enrollment unless it is post-transplant maintenance chemotherapy. Patients undergoing post-transplant maintenance chemotherapy are permitted to enroll.
- 1.4.2.2. The patient must have no evidence of disease progression or recurrence. Specifically, for the prostate cancer population, the patient must have no evidence of disease progression on their current ADT regimen at the time of enrollment.
- 1.4.2.3. The patient must not be a night shift worker, where night shift is defined as working a significant number of hours (i.e. more than half) between the hours of 11PM and 6AM on a regular basis.

1.5. *Intervention Plan*

- 1.5.1. Participants will be consented, enrolled, and randomized remotely with a Research Coordinator prior to beginning the trial. A review of inclusion/exclusion criteria will be conducted to determine the patient's eligibility for enrollment. Study procedures will be reviewed with the patient, and documentation of informed consent will be obtained. After signing the informed consent form (ICF) either in person or electronically using SignNow or other process approved by the University of Michigan IRBMED, patients will be assigned a unique study ID number in sequential order. Those who are found to be ineligible will be replaced.
- 1.5.2. After providing informed consent, the participant will be provided, in the clinic or via mail, a wearable device and a pair of glasses, which will be either blue-blocking (intervention group) or clear (control group). Both of these are described in detail in **Appendix A**. When both are in the participant's possession, the study coordinator will schedule a second meeting with the participant to onboard them to the specifics of the study.

- 1.5.3. The study coordinator will walk the participant through setting up the app and entering their Research ID number. They will ensure that the participant is able to connect to the wearable device via their phone and will explain to the subject that they should not wear the blue-blocking glasses while driving or if their vision will be impaired by them in a way that challenges their mobility.

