3. STUDY ENDPOINTS

3.1. *Primary Endpoint.* The primary endpoint is **fatigue**, as assessed by a daily fatigue questionnaire and a weekly 4-item PROMIS fatigue questionnaire.

3.2. *Secondary Endpoint.* The secondary endpoints are sleep disturbance, anxiety, depression, physical function and global health, as measured via the following PROMIS validated instruments:

- PROMIS Sleep Disturbance (8-item)
- PROMIS Anxiety (7-item)
- PROMIS Depression (8-item)
- PROMIS Physical Function (8-item)
- PROMIS Global Health (10-item)

3.3. *Exploratory Endpoints.*

3.3.1. Activity data. Patient activity (steps) and sleep will be measured continuously from the start to the end of the trial through wearable sensors.

3.3.2. Health care utilization data. Patient health care utilization data (e.g., total count of hospital days, emergency department visits, readmissions, and ambulatory care clinic visits) will be captured through the electronic health record as well as self-report (i.e., if the patient is readmitted at an outside hospital other than Michigan Medicine).

3.3.3. Sleep aid utilization data will be collected via self-report in the app once a week.

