5.14.2. Patient health care utilization. The total count of hospital days, ED visits, readmissions, and ambulatory care clinic visits during the trial, with adjustment for follow-up, will be compared between arms using a Poisson regression model, with adjustment for potential mediating or moderating effects of patient characteristics, if needed. The data will be captured at the time of PRO assessments.

5.14.3. Patient sleep aid utilization. The total number of sleep aids being used by the patients, as well as the types, will be collected via weekly surveys over the course of the trial.

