APPENDIX B: SYNC COMPONENTS

Study participants randomized to the Intervention Arm will use a version of SYNC that makes behavioral recommendations to correct circadian misalignment. Those in the Control Arm will use a “dummy” version of the app that makes behavioral recommendations that should minimally affect the circadian clock.

The full version of SYNC has the following features:

- Light exposure recommendations; e.g. times to sit near a window or go outside
- Light avoidance recommendations; e.g. times to wear blue-blocking glasses
- Caffeine avoidance recommendations
- Ideal times to sleep
- Ideal times to exercise for peak performance
- Ideal times to exercise to shift the circadian clock
- Surveys embedded for daily tracking of fatigue and other metrics
- Personalized educational information about the circadian clock

The dummy version of SYNC has the following features:

- Light exposure recommendations, timed to avoid shifting circadian rhythms
- Surveys embedded for daily tracking of fatigue and other metrics

The abovementioned recommendations are calculated using mathematical models of the circadian clock which read in data from the user’s wearable device. The times are expected to shift every day, as the user’s circadian clock shifts.

Sample behavioral recommendations from the full app include:

- *“Sit near a window or go outside from 8:30 am - 9:45 am”*
- *“Put on your blue-blocking glasses at 7:05 pm”*
- *“To fall asleep earlier tonight, do a workout between 6:45 am and 9:30 am”*
- *“Your peak window of athletic performance is from 7:45 pm - 9:45 pm”*
- *“Taking a nap from 1:00 - 1:45 pm today shouldn’t keep you from falling asleep tonight.”*

The dummy version of the app will make the following recommendations:

- *“Put on your study-provided glasses from 12:00 pm - 1:00 pm”*
- *“Be in a room with normal lighting from 1:00 pm - 1:30 pm”*

A screenshot of the app, currently in revision, is provided below for context:

9:41 

Task points: **Halfway there!**

 Progress Goal

Circadian state: In sync

 Learn more about how staying in sync helps you sleep! 

Daily Tasks

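### Exploratory objectives 1.3.3.1 and 1.3.3.2 ask for change by arm, but the plan defines no baseline period or change measure for activity or health care utilization

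*Combined protocol and SAP*

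**What the plan says.** Study Design 1.3.3.1 gives the activity objective as "Change in patient physical activity through physiological data capture using the wearable sensors in the control versus intervention arm". Study Design 1.3.3.2 reads "Change in patient health care utilization (e.g., total count of hospital days, readmissions, and ambulatory care clinic visits) in the control versus intervention arm". Neither says from when to when. The secondary objective just above them (1.3.2) does, naming baseline and the 12-week assessment. The synopsis is looser: "Exploratory objectives will be to assess: i) physical activity through physiological data capture using the wearable sensor".

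On data windows, 3.3.1 states: "Patient activity (steps) and sleep will be measured continuously from the start to the end of the trial through wearable sensors". Under Study Design 1.5.1 to 1.5.3, participants are randomized before the trial begins and receive the device and the arm-specific glasses after consent. Then "the study coordinator will schedule a second meeting with the participant to onboard them to the specifics of the study". At that meeting the app is set up, the research ID is entered and the device is connected. No period of wear without recommendations is described.

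On analysis, 5.14.1 derives motif and sleep variables from the accelerometer data and compares them by arm. Section 5.14.2 takes "The total count of hospital days, ED visits, readmissions, and ambulatory care clinic visits during the trial" into a Poisson regression, adjusted for follow-up and, if needed, for patient characteristics. Section 3.3.2 names the electronic health record, supplemented by self-report, as the source.

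**The concern.** An objective worded as change needs a starting value, and the analysis sections supply none. The wearable record begins with the trial, and the utilization count covers only the trial period. The analyst would therefore either report an on-trial difference under the label of change, or choose a reference period after the data are in.

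Two things are at stake. The first is interpretation: a within-arm statement that activity rose or visits fell after the intervention began has no planned basis. The second is precision: the sample mixes breast cancer, prostate cancer and transplant patients, and neither analysis commits to using a prior value or cancer population as a covariate. For utilization, the record that would supply the prior value is already the data source.

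**Working it through.** **Plan's own figures.** None is stated for these endpoints. The only sample-size figure (5.7) is for fatigue: 2 × (1.960 + 0.842)² / 0.5² = 62.8, so 63 per arm by the normal approximation. The exact two-sample t calculation gives 63.77, so 64, and 64 / 0.93 = 68.8, so 69. The plan's figures reproduce and do not bear on this point.

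**Objective against analysis.**

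| | Objective | Window of data | Planned analysis | Pre-intervention value |
|---|---|---|---|---|
| Activity | change by arm (1.3.3.1) | start to end of trial (3.3.1) | derived variables compared by arm (5.14.1) | none defined |
| Utilization | change by arm (1.3.3.2) | trial period (5.14.2) | Poisson regression by arm (5.14.2) | none defined |

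**What the planned contrast estimates.** Let Y be the on-trial mean and B a pre-intervention mean, with subscripts 1 (intervention) and 0 (control). The between-arm difference in change is

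(Y₁ − B₁) − (Y₀ − B₀) = (Y₁ − Y₀) − (B₁ − B₀).

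Randomization gives B₁ − B₀ an expectation of zero, so Y₁ − Y₀ is unbiased for the arm effect without B. What is lost is the within-arm change Y − B, and the ability to remove chance imbalance and between-patient variation in B.

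**If week 1 stands in for B.** Week 1 lies inside the 12-week intervention period. If the arm effect is δ₁ in week 1 and δ₁₂ in week 12, the contrast of changes has expectation δ₁₂ − δ₁. An effect that appeared at once and held steady would give δ − δ = 0. The quantity can be computed, but it is not change from before the intervention.

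**Precision (illustration only).** Assume a continuous outcome, equal variance before and on trial, and correlation r. The documents give no r. Relative to comparing on-trial values alone:

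| r (assumed) | Baseline as covariate, 1 − r² | Reduction in standard error | Change score, 2(1 − r) |
|---|---|---|---|
| 0.3 | 0.91 | 5% | 1.40 |
| 0.5 | 0.75 | 13% | 1.00 |
| 0.7 | 0.51 | 29% | 0.60 |
| 0.8 | 0.36 | 40% | 0.40 |

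The gain runs from slight to large depending on r. Below r = 0.5 a subtracted score is noisier than no baseline at all, whereas a covariate does not increase the variance in this calculation. The factors belong to linear adjustment and do not transfer to a Poisson model of counts, so no figure can be put on the utilization analysis.

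**The case against.** The strongest reply is that 1.3.3 is loosely worded and nothing more. The synopsis speaks only of assessing these outcomes, 5.14 compares arms, and randomization supports that comparison without a baseline. The endpoints are exploratory, with no power claim. Section 5.4 plans 23 patients from each cancer population in each arm, so cancer type should be about balanced. All of this stands, and it limits the point to the label and to precision.

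A reader might go further in four ways that the documents do not support.

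- *That neither change can be computed.* Activity is recorded continuously, so an early-to-late change is available, though with an on-treatment reference. The health record could supply prior utilization. Section 5.14.2 also has utilization captured when the patient-reported outcomes are, and 4.3 places one such assessment before the intervention. That fixes when data are collected, not a look-back window, but it does not rule one out.
- *That differences between patients overwhelm any arm effect.* The documents give no variance for activity or utilization.
- *That the first recommendations cannot be personalized.* Appendix B says recommendations are "calculated using mathematical models of the circadian clock which read in data from the user’s wearable device", but the documents do not say how the model is started or exactly when recommendations switch on. Section 4.3 has pre-intervention surveys completed in the app, so app setup need not coincide with the start of the intervention.
- *That daily fatigue has the same defect.* Its schedule is headed "Every day after starting the trial", but its objective is a difference between arms, and weekly PROMIS Fatigue supplies a first-day value with 7-day recall.

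**Conclusion.** The mismatch is real and modest. Both objectives ask for change by arm, and no baseline period, change measure or pre-intervention covariate is defined for either. The planned between-arm comparisons are valid by randomization; they answer a question about on-trial levels and counts.

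The cost is a mislabelled objective and some lost precision. The table above shows the possible range for a continuous outcome under assumed correlations; the documents give neither a correlation nor a variance from which to fix the actual loss. The conclusion rests on the text as available. The schedule diagram is not shown, so it could not be checked for a recommendation-free period; none is described in the procedures.

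**What to change.** **Utilization (5.14.2).** Extract the same health-record counts for a fixed window before enrolment, for example 12 weeks. Include the prior count and cancer population as covariates in the Poisson model, keeping the adjustment for follow-up, and let the slope on the prior count differ by cancer population. Do not subtract the prior count: the eligibility criteria set no minimum time since transplant, so the look-back for transplant patients may include the transplant admission, and a subtracted score would then largely reflect recovery from it. Word 1.3.3.2 to match, as a between-arm comparison of on-trial utilization adjusted for prior utilization.

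The cost is one more date range in an extraction already planned, with no patient burden. Care at outside hospitals before enrolment would be missed unless self-reported, so either ask about the same window at baseline or state the limitation. Section 5.3 says how late records may be accessed but not how far back; confirm that the look-back is covered.

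**Activity (5.14.1 and 1.3.3.1).** Include cancer population as a covariate, and restate the objective as the between-arm difference in level over weeks 1 to 12. If an early-to-late change is also reported, state that week 1 is on treatment. The cost is wording and one covariate.

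**Optional.** A recommendation-free run-in week in both arms would give a true wearable baseline. It adds a week per participant and a defined switch-on date. Background 1.6 and 1.8 describe a passive version of the app used earlier. This is a design trade-off for the investigators, and the point does not depend on it.
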